35894915	COVID-19 vaccine	covid-19 vaccine	Exposure	drug
35897994	COVID-19 vaccine Injectable Solution	covid-19 vaccine	Exposure	drug
36118948	COVID-19 vaccine, whole virus, inactivated, adjuvanted with Alum and CpG 1018	covid-19 vaccine	Exposure	drug
36118949	COVID-19 vaccine, recombinant, full-length nanoparticle spike (S) protein, adjuvanted with Matrix-M	covid-19 vaccine	Exposure	drug
36119720	COVID-19 vaccine, whole virus, inactivated, adjuvanted with Alum and CpG 1018 Injectable Suspension	covid-19 vaccine	Exposure	drug
36119721	COVID-19 vaccine, recombinant, full-length nanoparticle spike (S) protein, adjuvanted with Matrix-M Injectable Suspension	covid-19 vaccine	Exposure	drug
36119722	COVID-19 vaccine, recombinant, plant-derived Virus-Like Particle (VLP) spike (S) protein, adjuvanted with AS03 Injectable Suspension	covid-19 vaccine	Exposure	drug
36126197	COVID-19 vaccine, recombinant, plant-derived Virus-Like Particle (VLP) spike (S) protein, adjuvanted with AS03	covid-19 vaccine	Exposure	drug
724905	SARS-COV-2 (COVID-19) vaccine, vector non-replicating, recombinant spike protein-ChAdOx1, preservative free, 0.5 mL	covid-19 vaccine	Exposure	drug
724904	SARS-COV-2 (COVID-19) vaccine, UNSPECIFIED	covid-19 vaccine	Exposure	drug

APPENDIX I, TABLE 2: PRELIMINARY CONCEPTS FOR OUTCOMES

Concept ID	Concept name
Outcome	Cerebral venous sinus thrombosis (CVST)
4102202	Cerebral venous sinus thrombosis
4048786	Cerebral venous thrombosis of sigmoid sinus
4043735	Cerebral venous thrombosis of straight sinus
4111713	Non-pyogenic venous sinus thrombosis
314667	Nonpyogenic thrombosis of intracranial venous sinus
4116206	Septic thrombophlebitis of cavernous sinus
4121335	Septic thrombophlebitis of lateral sinus
4119136	Septic thrombophlebitis of sagittal sinus
4041680	Septic thrombophlebitis of sigmoid sinus
4100225	Thrombophlebitis lateral venous sinus
4217471	Thrombophlebitis of basilar sinus

	Phase II C3-001 – Study Protocol	
	Author(s): [name], [name]	Version: v3.1
	Dissemination level: public	

4104695	Thrombophlebitis of cavernous sinus
4167985	Thrombophlebitis of inferior sagittal sinus
764714	Thrombophlebitis of sigmoid sinus
4100224	Thrombophlebitis of superior longitudinal venous sinus
4098706	Thrombophlebitis of superior sagittal sinus
4277833	Thrombophlebitis of torcular Herophili
764710	Thrombophlebitis of transverse sinus
4228209	Thrombosis of basilar sinus
4234264	Thrombosis of cavernous venous sinus
4048890	Thrombosis of inferior sagittal sinus
4057329	Thrombosis of lateral venous sinus
4102203	Thrombosis of superior longitudinal sinus
4290940	Thrombosis of superior sagittal sinus
4079905	Thrombosis of torcular Herophili
4105338	Thrombosis transverse sinus
Outcome	DVT-narrow
762047	Acute bilateral thrombosis of subclavian veins
762148	Acute deep vein thrombosis of bilateral iliac veins
761444	Acute deep vein thrombosis of bilateral lower limbs following coronary artery bypass graft
35616028	Acute deep vein thrombosis of left iliac vein
35615035	Acute deep vein thrombosis of left lower limb following procedure
761416	Acute deep vein thrombosis of left upper limb following coronary artery bypass graft
35615031	Acute deep vein thrombosis of left upper limb following procedure
43531681	Acute deep vein thrombosis of lower limb
35616027	Acute deep vein thrombosis of right iliac vein
35615034	Acute deep vein thrombosis of right lower limb following procedure
761415	Acute deep vein thrombosis of right upper limb following coronary artery bypass graft
35615030	Acute deep vein thrombosis of right upper limb following procedure
44782746	Acute deep venous thrombosis
44782751	Acute deep venous thrombosis of axillary vein
762008	Acute deep venous thrombosis of bilateral axillary veins
760875	Acute deep venous thrombosis of bilateral calves
765155	Acute deep venous thrombosis of bilateral ileofemoral veins
762017	Acute deep venous thrombosis of bilateral internal jugular veins
762417	Acute deep venous thrombosis of bilateral legs
762020	Acute deep venous thrombosis of bilateral popliteal veins
765546	Acute deep venous thrombosis of bilateral tibial veins
762004	Acute deep venous thrombosis of both upper extremities
44782742	Acute deep venous thrombosis of calf

	Phase II C3-001 – Study Protocol	
	Author(s): [name], [name]	Version: v3.1
	Dissemination level: public	

44782747	Acute deep venous thrombosis of femoral vein
762015	Acute deep venous thrombosis of ileofemoral vein of left leg
765541	Acute deep venous thrombosis of ileofemoral vein of right lower extremity
44782748	Acute deep venous thrombosis of iliofemoral vein
44782752	Acute deep venous thrombosis of internal jugular vein
762009	Acute deep venous thrombosis of left axillary vein
760876	Acute deep venous thrombosis of left calf
765540	Acute deep venous thrombosis of left femoral vein
765922	Acute deep venous thrombosis of left internal jugular vein
762418	Acute deep venous thrombosis of left lower extremity
765537	Acute deep venous thrombosis of left upper extremity
44782767	Acute deep venous thrombosis of lower extremity as complication of procedure
46270071	Acute deep venous thrombosis of lower limb due to coronary artery bypass grafting
762022	Acute deep venous thrombosis of popliteal vein of right leg
44782743	Acute deep venous thrombosis of popliteal vein
762021	Acute deep venous thrombosis of popliteal vein of left leg
762010	Acute deep venous thrombosis of right axillary vein
760877	Acute deep venous thrombosis of right calf
762013	Acute deep venous thrombosis of right femoral vein
762018	Acute deep venous thrombosis of right internal jugular vein
762419	Acute deep venous thrombosis of right lower extremity
762005	Acute deep venous thrombosis of right upper extremity
44782745	Acute deep venous thrombosis of thigh
44782744	Acute deep venous thrombosis of tibial vein
762026	Acute deep venous thrombosis of tibial vein of left leg
765156	Acute deep venous thrombosis of tibial vein of right leg
44782421	Acute deep venous thrombosis of upper extremity
764016	Acute deep venous thrombosis of upper extremity after coronary artery bypass graft
44782766	Acute deep venous thrombosis of upper extremity as complication of procedure
762048	Acute thrombosis of left subclavian vein
45757410	Acute thrombosis of mesenteric vein
762049	Acute thrombosis of right subclavian vein
36712892	Acute thrombosis of splenic vein
44782762	Acute thrombosis of subclavian vein
37109253	Bilateral acute deep vein thrombosis of femoral veins
40478951	Bilateral deep vein thrombosis of lower extremities
4046884	Deep vein thrombosis of leg related to air travel
4133004	Deep venous thrombosis
4181315	Deep venous thrombosis associated with coronary artery bypass graft

	Phase II C3-001 – Study Protocol	
	Author(s): [name], [name]	Version: v3.1
	Dissemination level: public	

45773536	Deep venous thrombosis of femoropopliteal vein
763942	Deep venous thrombosis of left lower extremity
761980	Deep venous thrombosis of left upper extremity
443537	Deep venous thrombosis of lower extremity
4133975	Deep venous thrombosis of pelvic vein
40480555	Deep venous thrombosis of peroneal vein
4322565	Deep venous thrombosis of profunda femoris vein
763941	Deep venous thrombosis of right lower extremity
761928	Deep venous thrombosis of right upper extremity
4207899	Deep venous thrombosis of tibial vein
4028057	Deep venous thrombosis of upper extremity
193512	Embolism and thrombosis of the renal vein
435565	Embolism and thrombosis of the vena cava
4119760	Iliofemoral deep vein thrombosis
4124856	Inferior mesenteric vein thrombosis
4281689	Phlegmasia alba dolens
4284538	Phlegmasia cerulea dolens
4309333	Postoperative deep vein thrombosis
46285905	Provoked deep vein thrombosis
4033521	Splenic vein thrombosis
4055089	Superior mesenteric vein thrombosis
42538533	Thrombosis of iliac vein
44811347	Thrombosis of internal jugular vein
765049	Thrombosis of left peroneal vein
4317289	Thrombosis of mesenteric vein
4203836	Thrombosis of subclavian vein
4175649	Thrombosis of the popliteal vein
4153353	Traumatic thrombosis of axillary vein
46285904	Unprovoked deep vein thrombosis
4221821	Thrombophlebitis of deep veins of lower extremity
46271900	Recurrent deep vein thrombosis
4189004	Deep vein thrombosis of leg related to intravenous drug use
Outcome	SVT
4033521	Splenic vein thrombosis
36712892	Acute thrombosis of splenic vein
4033521	Splenic vein thrombosis
196715	Budd-Chiari syndrome
199837	Portal vein thrombosis
4317289	Thrombosis of mesenteric vein
4092406	Portal thrombophlebitis
36712892	Acute thrombosis of splenic vein

	Phase II C3-001 – Study Protocol	
	Author(s): [name], [name]	Version: v3.1
	Dissemination level: public	

4173167	Mesenteric embolus
4144032	Mesenteric thrombus and/or embolus
45757410	Acute thrombosis of mesenteric vein
45757409	Chronic thrombosis of mesenteric vein
4318407	Thrombophlebitis of mesenteric vein
4124856	Inferior mesenteric vein thrombosis
4055089	Superior mesenteric vein thrombosis
199837	Portal vein thrombosis
36717492	Acute occlusion of mesenteric vein
45757410	Acute thrombosis of mesenteric vein
4124856	Inferior mesenteric vein thrombosis
4055089	Superior mesenteric vein thrombosis
4317289	Thrombosis of mesenteric vein
45757409	Chronic thrombosis of mesenteric vein
4318407	Thrombophlebitis of mesenteric vein
4173167	Mesenteric embolus
4144032	Mesenteric thrombus and/or embolus
36717492	Acute occlusion of mesenteric vein
36712892	Acute thrombosis of splenic vein
196715	Budd-Chiari syndrome
35624285	Complete obstruction of hepatic portal vein
4301208	Hepatic vein thrombosis
37110194	Hepatic veno-occlusive disease with immunodeficiency syndrome
37109927	Obstruction of visceral vein
4238060	Portal vein obstruction
4033521	Splenic vein thrombosis
4277276	Veno-occlusive disease of the liver
37111372	Visceral venous thrombosis
36712891	Chronic thrombosis of splenic vein
Outcome	Pulmonary embolism
4120091	Acute massive pulmonary embolism
45768439	Acute pulmonary embolism
45768888	Acute pulmonary thromboembolism
4309039	Hemorrhagic pulmonary infarction
762808	Infarction of lung due to embolus
40480461	Infarction of lung due to iatrogenic pulmonary embolism
4108681	Postoperative pulmonary embolus
4091708	Pulmonary air embolism
440417	Pulmonary embolism
37109911	Pulmonary embolism due to and following acute myocardial infarction
37016922	Pulmonary embolism on long-term anticoagulation therapy

	Phase II C3-001 – Study Protocol	
	Author(s): [name], [name]	Version: v3.1
	Dissemination level: public	

43530605	Pulmonary embolism with pulmonary infarction
4119608	Pulmonary fat embolism
254662	Pulmonary infarction
4253796	Pulmonary microemboli
45766471	Pulmonary oil microembolism
4121618	Pulmonary thromboembolism
4119610	Pulmonary tumor embolism
4119607	Subacute massive pulmonary embolism
4119609	Subacute pulmonary fat embolism
4236271	Recurrent pulmonary embolism
Outcome	Ischemic stroke
4045735	Anterior cerebral circulation infarction
4031045	Anterior choroidal artery syndrome
761110	Bilateral cerebral infarction due to precerebral arterial occlusion
4110189	Cerebral infarct due to thrombosis of precerebral arteries
443454	Cerebral infarction
762951	Cerebral infarction due to anterior cerebral artery occlusion
765515	Cerebral infarction due to basilar artery stenosis
43530683	Cerebral infarction due to carotid artery occlusion
762933	Cerebral infarction due to cerebral artery occlusion
762937	Cerebral infarction due to cerebral venous thrombosis
4111714	Cerebral infarction due to cerebral venous thrombosis, non-pyogenic
4108356	Cerebral infarction due to embolism of cerebral arteries
45772786	Cerebral infarction due to embolism of middle cerebral artery
4110190	Cerebral infarction due to embolism of precerebral arteries
762935	Cerebral infarction due to internal carotid artery occlusion
763015	Cerebral infarction due to middle cerebral artery occlusion
46273649	Cerebral infarction due to occlusion of basilar artery
35610084	Cerebral infarction due to occlusion of cerebral artery
46270031	Cerebral infarction due to occlusion of precerebral artery
762934	Cerebral infarction due to posterior cerebral artery occlusion
43531607	Cerebral infarction due to stenosis of carotid artery
35610085	Cerebral infarction due to stenosis of cerebral artery
46270381	Cerebral infarction due to stenosis of precerebral artery
4110192	Cerebral infarction due to thrombosis of cerebral arteries
45767658	Cerebral infarction due to thrombosis of middle cerebral artery
44782773	Cerebral infarction due to vertebral artery occlusion
46270380	Cerebral infarction due to vertebral artery stenosis
37110678	Cerebral ischemic stroke due to occlusion of extracranial large artery
37110679	Cerebral ischemic stroke due to stenosis of extracranial large artery
4043731	Infarction - precerebral

	Phase II C3-001 – Study Protocol	
	Author(s): [name], [name]	Version: v3.1
	Dissemination level: public	

4131383	Infarction of basal ganglia
4046237	Infarction of optic radiation
4119140	Infarction of visual cortex
4141405	Left sided cerebral infarction
37116473	Multifocal cerebral infarction due to and following procedure on cardiovascular system
4077086	Occipital cerebral infarction
4046359	Partial anterior cerebral circulation infarction
4319146	Pituitary infarction
4146185	Right sided cerebral infarction
36717605	Silent cerebral infarct
4142739	Thalamic infarction
4046358	Total anterior cerebral circulation infarction
372924	Cerebral artery occlusion
Outcome	Myocardial infarction
4119457	Acute Q wave infarction - anterolateral
4119943	Acute Q wave infarction - anteroseptal
4121464	Acute Q wave infarction - inferior
4121465	Acute Q wave infarction - inferolateral
4124684	Acute Q wave infarction - lateral
4119948	Acute Q wave infarction - widespread
4126801	Acute Q wave myocardial infarction
4296653	Acute ST segment elevation myocardial infarction
46270162	Acute ST segment elevation myocardial infarction due to left coronary artery occlusion
761737	Acute ST segment elevation myocardial infarction due to occlusion of circumflex coronary artery
46270163	Acute ST segment elevation myocardial infarction due to right coronary artery occlusion
43020460	Acute ST segment elevation myocardial infarction involving left anterior descending coronary artery
45766076	Acute ST segment elevation myocardial infarction of anterior wall involving right ventricle
761736	Acute ST segment elevation myocardial infarction of anteroapical wall
46270159	Acute ST segment elevation myocardial infarction of anterolateral wall
46270160	Acute ST segment elevation myocardial infarction of anteroseptal wall
45766116	Acute ST segment elevation myocardial infarction of inferior wall
45766151	Acute ST segment elevation myocardial infarction of inferior wall involving right ventricle
35611570	Acute ST segment elevation myocardial infarction of inferolateral wall
35611571	Acute ST segment elevation myocardial infarction of inferoposterior wall
46274044	Acute ST segment elevation myocardial infarction of lateral wall
46270161	Acute ST segment elevation myocardial infarction of posterior wall
46273495	Acute ST segment elevation myocardial infarction of posterobasal wall

	Phase II C3-001 – Study Protocol	
	Author(s): [name], [name]	Version: v3.1
	Dissemination level: public	

46270158	Acute ST segment elevation myocardial infarction of posterolateral wall
46270164	Acute ST segment elevation myocardial infarction of septum
45766075	Acute anterior ST segment elevation myocardial infarction
4178129	Acute anteroapical myocardial infarction
4267568	Acute anteroseptal myocardial infarction
312327	Acute myocardial infarction
44782769	Acute myocardial infarction due to left coronary artery occlusion
44782712	Acute myocardial infarction due to right coronary artery occlusion
45766115	Acute myocardial infarction during procedure
434376	Acute myocardial infarction of anterior wall
45766150	Acute myocardial infarction of anterior wall involving right ventricle
438438	Acute myocardial infarction of anterolateral wall
4243372	Acute myocardial infarction of apical-lateral wall
4108669	Acute myocardial infarction of atrium
4151046	Acute myocardial infarction of basal-lateral wall
4275436	Acute myocardial infarction of high lateral wall
438170	Acute myocardial infarction of inferior wall
45771322	Acute myocardial infarction of inferior wall involving right ventricle
438447	Acute myocardial infarction of inferolateral wall
441579	Acute myocardial infarction of inferoposterior wall
436706	Acute myocardial infarction of lateral wall
4324413	Acute myocardial infarction of posterobasal wall
4051874	Acute myocardial infarction of posterolateral wall
4303359	Acute myocardial infarction of septum
4147223	Acute myocardial infarction with rupture of ventricle
4145721	Acute non-Q wave infarction
4119944	Acute non-Q wave infarction - anterolateral
4119456	Acute non-Q wave infarction - anteroseptal
4119945	Acute non-Q wave infarction - inferior
4119946	Acute non-Q wave infarction - inferolateral
4121466	Acute non-Q wave infarction - lateral
4124685	Acute non-Q wave infarction - widespread
4270024	Acute non-ST segment elevation myocardial infarction
35610091	Acute nontransmural myocardial infarction
319039	Acute posterior myocardial infarction
444406	Acute subendocardial infarction
35610093	Acute transmural myocardial infarction
4119947	Acute widespread myocardial infarction
37109912	Arrhythmia due to and following acute myocardial infarction
438172	Atrial septal defect due to and following acute myocardial infarction
4124687	Cardiac rupture due to and following acute myocardial infarction

	Phase II C3-001 – Study Protocol	
	Author(s): [name], [name]	Version: v3.1
	Dissemination level: public	

4215259	First myocardial infarction
4108678	Hemopericardium due to and following acute myocardial infarction
4173632	Microinfarct of heart
45771327	Mitral valve regurgitation due to acute myocardial infarction with papillary muscle and chordal rupture
45766214	Mitral valve regurgitation due to acute myocardial infarction without papillary muscle and chordal rupture
45766212	Mitral valve regurgitation due to and following acute myocardial infarction
4323202	Mixed myocardial ischemia and infarction
4329847	Myocardial infarction
37309626	Myocardial infarction due to demand ischemia
4170094	Myocardial infarction in recovery phase
4200113	Non-Q wave myocardial infarction
4030582	Postoperative myocardial infarction
35610087	Postoperative nontransmural myocardial infarction
4206867	Postoperative subendocardial myocardial infarction
35610089	Postoperative transmural myocardial infarction
4207921	Postoperative transmural myocardial infarction of anterior wall
4209541	Postoperative transmural myocardial infarction of inferior wall
37109911	Pulmonary embolism due to and following acute myocardial infarction
4108679	Rupture of cardiac wall without hemopericardium as current complication following acute myocardial infarction
4108219	Rupture of chordae tendinae due to and following acute myocardial infarction
4124686	Silent myocardial infarction
765132	Subendocardial myocardial infarction
45766114	Subsequent ST segment elevation myocardial infarction
45766113	Subsequent ST segment elevation myocardial infarction of anterior wall
45773170	Subsequent ST segment elevation myocardial infarction of inferior wall
4108217	Subsequent myocardial infarction
4108677	Subsequent myocardial infarction of anterior wall
4108218	Subsequent myocardial infarction of inferior wall
45766241	Subsequent non-ST segment elevation myocardial infarction
4108680	Thrombosis of atrium, auricular appendage, and ventricle due to and following acute myocardial infarction
439693	True posterior myocardial infarction
37109910	Ventricular aneurysm due to and following acute myocardial infarction
Outcome	Intestinal infarction
4195665	Gastrointestinal tract vascular insufficiency
4148299	Ischemic colitis
4173167	Mesenteric embolus
4317289	Thrombosis of mesenteric vein
4319280	Acute bowel infarction
4144032	Mesenteric thrombus and/or embolus

	Phase II C3-001 – Study Protocol	
	Author(s): [name], [name]	Version: v3.1
	Dissemination level: public	

45757410	Acute thrombosis of mesenteric vein
45757409	Chronic thrombosis of mesenteric vein
44811741	Acute ischaemia of large intestine
44811740	Acute ischaemia of small intestine
37117790	Insufficiency of mesenteric artery
37016198	Epiplaic appendagitis
35622081	Nongangrenous ischemic colitis
35622080	Gangrenous ischemic colitis
4345926	Abdominal angina
4342767	Transient ischemic colitis
4341648	Hemorrhagic infarction of intestine
4341646	Occlusive mesenteric ischemia
4340939	Non-occlusive mesenteric ischemia
4340378	Transmural infarction of intestine
4340375	Focal segmental ischemia of small intestine
4318537	Large bowel gangrene
4318407	Thrombophlebitis of mesenteric vein
4240850	Acute ischemic enterocolitis
4239942	Embolic mesenteric infarction
4237654	Ischemic enterocolitis
4215949	Nonocclusive intestinal infarction
4214720	Thrombotic mesenteric infarction
4192856	Acute ischemic colitis
4188336	Chronic ischemic enterocolitis
4174014	Inferior mesenteric artery embolus
4149013	Mesenteric infarction
4148257	Chronic gastrointestinal tract vascular insufficiency
4148256	Acute GIT vascular insufficiency
4124856	Inferior mesenteric vein thrombosis
4055089	Superior mesenteric vein thrombosis
4055025	Superior mesenteric artery embolus
4045408	Ischemic stricture of intestine
201894	Acute vascular insufficiency of intestine
192673	Vascular insufficiency of intestine

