Covid-19 intensive care use (cohort 4)	intensive services initiated during a hospitalisation as described in the “covid-19 hospitalized” criterion	before	During hospitalization	Intensive care	SNOMED	n/a	Individuals who met the “covid-19 hospitalized” criteria	n/a	n/a
Covid-19 vaccinated (cohort 5)	a vaccination record identified by brand (with the index date the date of vaccination record)	before	n/a	Primary care	RxNorm	n/a	All individuals within the selected databases	n/a	n/a

¹ IP = inpatient, OP = outpatient, ED = emergency department, OT = other, n/a = not applicable

² Specify whether a diagnosis code is required to be in the primary position (main reason for encounter)

Table 4. Operational Definitions of Exclusion Criteria

Criterion	Details	Order of application	Assessment window	Care Setting¹	Code Type	Diagnosis position²	Applied to study population^s	Measurement characteristic^{s/}	Source for algorithm
Prior covid-19 (cohort 2-4)	have no positive test result for SARS-CoV-2 or clinical diagnosis of COVID-19 within 3 months prior to the index date.	After	[-91,0]	OP,IP	SNOMED, RxNorm	n/a	SARS-CoV-2 infected, hospitalized (cohorts 2, 3, 4)	n/a	n/a

	Phase II C3-001 – Study Protocol	
	Author(s): [name], [name]	Version: v3.1
	Dissemination level: public	

Hospitalization (cohort 3)	have no diagnosis of COVID-19 or a positive test result for SARS-CoV-2 between 3 months and 3 weeks prior to index date. Have no COVID-19 hospitalisation within 3 weeks prior to the index date.	After	Covid-19 [-91,-21]; Hospitalization [-21,0]	IP	SNOMED	n/a	Covid-19 hospitalized (cohorts 3, 4)	n/a	n/a
Vaccinated (cohort 5)	No vaccine records in the 21 days prior to index vaccine	after	[-21 , 0]	OP	RxNorm	n/a	Vaccinated (cohort 5)	n/a	n/a
Prior outcomes all cohorts)	Exclude people with the outcome of interests during the 183 day prior to index. (primary analysis, different washout period will be applied in sensitivity analysis)		[-183,0]	IP, OP	SNOMED	n/a	(cohorts 1-5)	n/a	n/a

1 IP = inpatient, OP = outpatient, ED = emergency department, OT = other, n/a = not applicable

2 Specify whether a diagnosis code is required to be in the primary position (main reason for encounter)

Criterion: A brief text entry naming the in- and/or exclusion criterion (e.g. age, sex, atrial fibrillation)

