8.6.2. Outcomes

Venous thromboembolic events

In the primary analysis, venous thromboembolic events will be identified by diagnostic codes for pulmonary embolism or deep vein thrombosis. In a secondary analysis pulmonary embolism and deep vein thrombosis will be assessed separately. We will also assess portal vein thrombosis, splanchnic venous thrombosis (SVT) and cerebral venous sinus thrombosis separately.

Arterial thromboembolic events

In the primary analysis, arterial thromboembolic events will be identified by an acute myocardial infarction or acute ischemic stroke. In a secondary analysis acute myocardial infarction and acute ischemic stroke will be assessed separately. We also identify stroke in general, for which we will include both ischemic, haemorrhagic and non-specifically recorded stroke.

Cardiovascular events

Instances of heart failure, cardiac arrhythmia, and angina will be identified. In addition, major cardiovascular events (MACE) will be identified by heart failure, acute myocardial infarction, or stroke, or the occurrence of sudden cardiac death. As a sensitivity analysis, we will require that events were identified by hospitalisation admission or discharge records.

Table 6. Operational Definitions of Outcome

Outcome name	Details	Primary outcome?	Type of outcome	Washout window	Care Settings ¹	Code Type	Diagnosis Position ²	Applied to study:	Measurement characteristics/validation	Source of algorithm
Venous thromboembolic events	venous thromboembolic events will be identified by diagnostic codes for pulmonary embolism or deep vein thrombosis	Yes	Binary, time-to-event	[-183,-1]	IP,OP	SNOMED	n/a	All included cohorts	n/a	n/a
Arterial thromboembolic events	arterial thromboembolic events will be identified by an acute myocardial infarction or acute ischemic stroke	Yes	Binary, time-to-event	[-183,-1]	IP,OP	SNOMED	n/a	All included cohorts	n/a	n/a
Cardiovascular events	heart failure, cardiac arrhythmia, and angina will be identified.	No	Binary, time-to-event	[-183,-1]	IP,OP	SNOMED	n/a	All included cohorts	n/a	n/a
major cardiovascular events (MACE)	MACE will be identified by heart failure, acute myocardial infarction, or stroke, or the occurrence of sudden cardiac death.	No	Binary, time-to-event	[-1835,-1]	IP,OP	SNOMED	n/a	All included cohorts	n/a	n/a
pulmonary embolism		No	Binary, time-to-event	[-183,-1]	IP,OP	SNOMED	n/a	All included cohorts	n/a	n/a

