8.7 Study size

For each database, all individuals that satisfy the eligibility criteria for a study cohort will be included.

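### The preliminary SVT code list counts chronic and hepatic veno-occlusive concepts as new splanchnic venous thrombosis, and portal vein thrombosis has no list of its own

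*Protocol*

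**What the plan says.** Section 8.6.2 places SVT under venous thromboembolic events, as a secondary outcome: "We will also assess portal vein thrombosis, splanchnic venous thrombosis (SVT) and cerebral venous sinus thrombosis separately". Table 6 gives portal vein thrombosis and SVT a row each, both time-to-event, not primary, with a washout from day -183 to day -1. The exclusion criteria in Section 8.5 apply the same idea to all cohorts: "Exclude people with the outcome of interests during the 183 day prior to index". Section 8.8.5 compares the vaccinated and COVID-19 cohorts with the background population by SIR. Table 8 carries the same analysis over to the secondary outcomes.

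Appendix I, Table 2 is headed as preliminary. Its SVT block includes "Chronic thrombosis of splenic vein" (36712891) and its mesenteric counterpart (45757409). It includes "Hepatic veno-occlusive disease with immunodeficiency syndrome" (37110194) and a second veno-occlusive liver concept (4277276). It also includes "Mesenteric embolus" (4173167) and "Mesenteric thrombus and/or embolus" (4144032). Portal vein thrombosis (199837) and portal thrombophlebitis (4092406) are in the same block, and Table 2 has no portal vein block. The note after Appendix I, Table 4 says that CohortDiagnostics will be run before the sets are finalised and may prompt changes.

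**The concern.** An SIR for SVT is meant to describe new clots in the splanchnic veins after infection or vaccination. A code for long-standing thrombosis does not describe a new clot, and a veno-occlusive liver code does not state a clot at all. If such codes count as events and are unrelated to exposure, they add about equally to observed and expected counts and move the ratio towards 1. In a safety comparison, that is the direction that hides a signal. Table 8 reports finer strata only when there are more than five events, so such codes can also decide which strata are shown.

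The portal vein point is separate. The plan promises a result for an outcome with no printed code set. Any set drawn from the SVT block would be a subset of SVT, and the protocol does not say so.

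**Working it through.** **1. Inputs.** The SVT, DVT-narrow and Intestinal infarction blocks of Appendix I, Table 2, and the washout in Table 6. There is no stated figure to reproduce. Section 8.7 gives no sample-size calculation ("all individuals that satisfy the eligibility criteria for a study cohort will be included"), and Table 1 gives feasibility counts of disease for VTE only.

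**2. Count.** The SVT block has 37 rows. Removing repeated IDs leaves 22 distinct concepts.

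| Group | IDs | Distinct concepts |
|---|---|---|
| Chronic by name | 45757409, 36712891 | 2 |
| Hepatic veno-occlusive, no thrombosis in the name | 4277276, 37110194 | 2 |
| No vessel named | 4173167, 4144032 | 2 |
| Remainder | | 22 - 6 = 16 |

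The first two groups are 4 of 22 concepts (18%). All three are 6 of 22 (27%). These are shares of concepts, not of events.

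**3. Does the washout protect against the chronic codes?** The rule removes people with a recorded outcome in the 183 days before index. Someone with no SVT code in that window, whose chronic code is first recorded after index, passes the exclusion and counts as an incident event. The any-time washout in Table 9 does not change this, because it too acts only on codes recorded before index.

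**4. Comparison with the protocol's other lists.** DVT-narrow covers mesenteric and splenic veins with six concepts that also appear under SVT (4033521, 36712892, 4317289, 45757410, 4124856, 4055089). It contains neither chronic code and neither embolus code. For the same vessels, the protocol's other venous list already leaves out four of the six concepts above.

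The Intestinal infarction block contains both embolus codes. It also contains concepts that name an artery, such as "Superior mesenteric artery embolus" (4055025), and six that name mesenteric veins. The concepts that name an artery (4055025, 4174014) are not in the SVT block. Membership of the Intestinal infarction block therefore does not show which vessel the two embolus codes refer to.

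**5. Effect on the SIR.** Let S be the SIR for true new SVT and f the share of *expected* events that come from codes unrelated to exposure (SIR 1 for those codes). Then

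SIR_obs = S(1 - f) + f.

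No f is given, so the values below are assumed, for illustration only.

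| f | S = 2 | S = 3 |
|---|---|---|
| 0.05 | 1.95 | 2.90 |
| 0.10 | 1.90 | 2.80 |
| 0.20 | 1.80 | 2.60 |
| 0.30 | 1.70 | 2.40 |

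Worked case: S = 3, f = 0.20 gives 3 × 0.80 + 0.20 = 2.60.

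The definition of f matters. If the share is g of the *observed* events, the formula is SIR_obs = S/(gS + 1 - g). With S = 3 and g = 0.20 this is 3/(0.60 + 0.80) = 2.14. Any later estimate from code counts must state which share it uses.

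**6. After the change.** Removing the chronic and veno-occlusive concepts leaves 22 - 4 = 18. The run without the two embolus codes has 16.

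**The case against.** The best defence is that the list is preliminary and that a diagnostic step is planned before it is fixed. That is so, and the mixing follows only if the list is run as printed. But the planned step looks at code counts and patient characteristics. It commits to no removal and does not clearly supply the missing portal vein set.

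A second defence is that SVT is secondary and that the choice of codes trades sensitivity against specificity. This stands, and it keeps the point at low severity. It also limits how far names alone can decide: the SVT block holds three concepts that name obstruction without thrombosis (35624285, 37109927, 4238060), and they are not counted here. The chronic codes are the clearest mismatch, because they contradict the incident definition by name.

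Third, the portal vein belongs to the splanchnic system, so holding its codes in SVT is not in itself an error. Section 8.6.2 also has pulmonary embolism and deep vein thrombosis assessed separately while both stay within VTE. Table 2 also lacks blocks for heart failure, arrhythmia, angina and general stroke, so the gap is not special to SVT. What remains is that portal vein thrombosis has no printed set and that the nesting is not stated.

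A reader might go further and infer that SVT reports arterial disease as venous. The document does not support that: the two embolus names give no vessel, and the concepts that do name arteries are absent from the list. It also does not show that veno-occlusive codes concentrate in the immunocompromised stratum, since only one of the two mentions immunodeficiency.

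**Conclusion.** The point holds as a mismatch between definition and code list. Four of 22 concepts would count as incident SVT although two are chronic by name and two state no thrombosis. Two more are unspecific as to vessel, and portal vein thrombosis has no set. The effect on the SIR is towards 1 on the assumption that the extra codes are unrelated to exposure; if they are related to it, the direction is not determined. The size cannot be derived, because the document gives no event counts by code, and 27% of concepts must not be read as 27% of events. The point concerns the SVT and portal vein outcomes only and makes no claim about the primary VTE and ATE results. Severity is low.

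**What to change.** Before the concept sets in Appendix I, Table 2 are finalised:

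- Take 45757409 and 36712891 out of the SVT event set and use them only to identify prior disease in the washout. DVT-narrow already omits them.
- Remove 4277276 and 37110194 from the SVT event set.
- Run SVT with and without 4173167 and 4144032 as a sensitivity analysis.
- Add a portal vein thrombosis set (at least 199837 and 4092406). Either state that it is nested in SVT or report SVT with and without portal vein events.
- Keep the printed list as a further sensitivity run.

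The cost is an edit to one preliminary list, one new short list and a few extra runs. Section 5 still shows the analytical code as to be confirmed. The small downside is that a few true events may leave the main set, but they stay visible in the run of the printed list.
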